	
dose. Supportive safety analyses will be carried out on the SAS2 according to the dose of apaglutide received.
 
Analysis of Secondary Endpoints
 
Day 56 lower GI-aGVHD responses will be summarized and analyzed formally using Bayesian methods. In the Bayesian analyses, the response rates will be modelled by Beta distributions presenting the mean of the Beta distributions-associated with 90% credible intervals. The differences in response rates will be taken as the difference in mean response rates of the distributions on apaglutide with respect to BAT. The associated 90% credible interval will be computed using simulations of the respective distributions.
 
Secondary endpoints measured as response/non-response will be analyzed in the same fashion as described above. If prior data for BAT is not available for a given time point, then only the apaglutide data will be presented.
 
Secondary endpoints measured as time-to-event will be summarized using Kaplan-Meier analysis. Where there are competing risks, time-to-event data will also be summarized using cumulative incidence. The median time-to-event will be presented where possible, along with the associated 90% confidence interval. For comparison to BAT where prior data exist, the distribution of time-to-event will be modelled via the inverse gamma distribution, and thus compared on a Bayesian basis.
 
Secondary endpoints will be summarized descriptively in the LBW Analysis Set.
 
Exploratory Endpoints
 
These endpoints will also be summarized descriptively in both the FAS and the LBW Analysis Sets.
 
Analysis of Safety Endpoints
 
All safety data will be summarized by apaglutide dose level for both SAS1 and SAS2.
 
Adverse Events
 
All AESIs, treatment-emergent AEs (TEAEs), serious AEs, AEs leading to discontinuation, AEs leading to death, and laboratory abnormalities will be summarized by apaglutide dose level, severity, and relationship to treatment. Adverse event data will be coded using the Medical Dictionary for Regulatory Activities (MedDRA) and presented by SOC and Preferred Term (PT).

--	---

TMP no.: TMP-CD-04_1
Version no.: 1.0
TMP effective date: 10-Oct-2019

Proof-of-concept trial of apaglutide in GVHD

[figure not shown]

Good Clinical Practice statement:

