1.5.2.2 Secondary Endpoints

- Overall response rate (PR and CR) at Day 56 on the lower GI tract MAGIC score
- Overall response rate (PR and CR) at Days 14, 28, 91, 119, 147, and 182 on the lower GI tract MAGIC score
- Overall response rate (PR and CR) at Days 14, 28, 56, 91, 119, 147, and 182 by organ system (skin, lower and upper GI tract, and liver) on the total MAGIC score
- Proportion of all subjects who achieve a CR or PR at Day 28 and maintain a CR or PR at Day 56
- Duration of response from Day 56 (median and range) on the total MAGIC score where duration of response is defined as the interval from the Day 56 response (PR and CR) to death or new systemic therapy for aGVHD (including an increase in steroids >2 mg/kg/day methylprednisolone [MP] equivalent), whichever occurs first, with at least 182 days of follow-up
- Duration of response from Day 28 (median and range) on the total MAGIC score where duration of response is defined as the interval from the Day 28 response (PR and CR) to death or new systemic therapy for aGVHD (including an increase in steroids >2 mg/kg/day MP equivalent), whichever occurs first, with at least 182 days of follow-up
- Individual duration of lower GI response (according to the MAGIC score) counted from the first response to return to baseline or worse
- Individual duration of lower GI response (according to the MAGIC score) in subjects that were re-treated with apaglutide because of a lower GI-aGVHD flare, counted from the first response after apaglutide restart to return to baseline or worse
- Time to partial lower GI-aGVHD response (median and range) as defined by the MAGIC score
- Time to complete lower GI-aGVHD response (median and range) as defined by the MAGIC score
- Best overall response defined as overall response (PR or CR) at any time point up to and including Day 91 and before the start of additional systemic therapy for lower GI-aGVHD
- Failure-free survival up to 2 years post-first dose of apaglutide
- Non-relapse mortality up to 2 years post-first dose of apaglutide
- Incidence of malignancy relapse up to 2 years post-first dose of apaglutide
- Overall survival up to 2 years post-first dose of apaglutide

- Incidence of graft failure up to 2 years post-first dose of apaglutide
- Incidence of lower GI-aGVHD flare up to Day 182 after the first apaglutide dose following earlier cessation due to complete lower GI-aGVHD response

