7.8.2 Other Secondary Endpoints

Secondary endpoints will be summarized descriptively in the FAS. These endpoints are listed in Section 1.5.2.2.

Secondary endpoints assessed as binary responses will be summarized and analyzed in the same fashion as outlined above; if prior data for BAT are not available for a given time point, then only the apaglutide data will be presented.

Subjects with missing data such that response cannot be determined will be included in the analyses as non-responders. Again, supportive analyses of the secondary endpoints will be performed based only on those subjects with non-missing secondary endpoint data consistent with a missing at random assumption.

Secondary endpoints assessed as time-to-event endpoints will be summarized using Kaplan-Meier analysis. The median time duration of response will be presented where possible, along with the range and the associated 90% confidence interval. For comparison to BAT where prior data exist on duration of response, the distribution duration of response will be modelled via the inverse gamma distribution and thus compared on a Bayesian basis.

Where there are competing risks, time to event data will also be summarized using cumulative incidence. For endpoints like graft failure and NRM, subjects who die prior to reaching either endpoint will be right censored at the time of death. For comparison to BAT where prior data exist, for example for FFS, the distribution of mean time to event will be modelled via the inverse gamma distribution and thus compared on a Bayesian basis. Similarly, the distribution of event rates will be modelled via a gamma distribution and compared on a Bayesian basis.

Further details of these analyses will be outlined in the SAP.

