#### 4.1.2 *Handling of Dropouts and Missing Data*

Unless specified otherwise, missing data values will be recorded as missing and will not be imputed for the statistical analysis. Only observed data values will be used for the reporting of descriptive statistics.

Subjects with missing data such that the response, for instance the Day 56 lower GI response, cannot be determined will be included in the analysis as non-responders, consistent with intent-to-treat principle. The details for handling missing data and intercurrent events are specified in the estimand description in Section 4.3.9.2.

Censoring for time-to-event endpoint will be described for each endpoint separately.

In cases of missing or incomplete dates (e.g. AE and concomitant medications), the missing component(s) will be assumed as the most conservative value possible, taking the worst-case approach. Thus, an adverse event will be considered a treatment emergent adverse event (TEAE) unless the recorded dates conclusively prove otherwise. For example, if the start date of an AE is missing and the stop date either falls after the first dose of apraglutide or missing, then the AE will be considered a TEAE. When partial dates are present in the data, both a partial start date and/or a partial stop date will be evaluated to determine whether it can be conclusively established that the AE started prior to the start of apraglutide or stopped prior to the start of apraglutide. If the above cannot be conclusively established based on partial and/or present dates, then the AE will be considered TEAE.

For classification of prior and concomitant medications, the same conservative convention described above will be applied for handing missing or partial medication dates, and medications will be considered concomitant if it cannot be conclusively established whether or not they were taken at any point after the start of apraglutide.

If “Relationship to trial medication” field from the original case report forms (eCRFs) for an AE is missing, it will be imputed as “Definitely Related”.

In case of missing normal ranges for laboratory results, the normal ranges will be imputed using literature references (such as Merck, 2021) in the corresponding ADaM dataset for analysis purpose.

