**Table 4-3: Date of Event or Censoring for Duration of Lower GI Response**

Situation	Date of event or censoring	Outcome	Event Description or Censoring Reason
Lower GI MAGIC score SD/PD before additional systemic therapy for aGVHD	First MAGIC assessment showing SD or PD, whichever occurs first	Event	SD/PD
Death without Lower GI MAGIC score SD/PD and not receiving additional systemic therapy for aGVHD	Date of death	Event	Death
Missing lower GI MAGIC assessment	Date of last evaluable MAGIC assessment before the first missed visit	Event	Missing visit
Additional systemic therapy for aGVHD used for any earlier progression, mixed response or stable aGVHD.	Date of last evaluable MAGIC assessment before additional systemic therapy for aGVHD	Event	Treatment Failure
Alive and without: Lower GI MAGIC score SD/PD, or missing, or initiation of additional systemic therapy for aGVHD	Date of last evaluable MAGIC assessment	Censored	Clinical cut-off date

Duration of Lower GI response will be summarized using Kaplan-Meier estimator. The number and percentage of subjects experiencing an event, and subjects censored will be summarized by apraglutide dose levels and in total. The median time-to-event will be presented where possible, along with the range and the associated two-sided 95% Brookmeyer-Crowley confidence interval. The event-free rate with 95% CI using Greenwood's formula will be provided for selected time points (e.g., 1, 3, 6, 12 and 24 months). Plots of the Kaplan-Meier estimate for the duration of Lower GI response will be presented by apraglutide dose levels and in total.

4.3.9.8 *Time to partial and complete lower GI-aGVHD response as defined by the MAGIC score*

Time to partial lower GI-aGVHD response is defined as the time from the first injection of apraglutide to the first partial response lower GI assessment according to MAGIC score. This is only defined for subjects with partial response. The ICE events and strategies defined in section 4.3.9.2 will be applied consistently for the estimation of CR and PR.

Time to complete lower GI-aGVHD response is defined as the time from the first injection of apaglutide to first complete response lower GI assessment according to the MAGIC score. This is only defined for subjects with complete response.

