The time to partial or complete lower GI-aGVHD response will be summarized by apaglutide dose levels and in total using descriptive statistics including number and percentage of subjects with partial and complete response, the arithmetic mean, standard deviation (sd), median, first and third quartiles (Q1, Q3), minimum, and maximum.

*4.3.9.9 Duration of response from Day 28 or Day 56 on the total MAGIC score*

Duration of response from Day 28 (resp. 56) on the total MAGIC score is defined as the interval from the Day 28 (resp. 56) response (PR and CR) to death or new systemic therapy for aGVHD (including an increase in steroids >2 mg/kg/day MP equivalent), whichever occurs first, with at least 182 days of follow-up. This is only defined for subjects with partial or complete response at Day 28 (resp. 56).

Subject for which neither "new systemic therapy for aGVHD" or "dead" event occurs will be right censored at their last follow-up visit.

Duration of response from Day 28 (resp. 56) on the total MAGIC will be summarized using Kaplan-Meier estimator. The number and percentage of subjects experiencing an event, and subjects censored will be summarized by apaglutide dose levels and in total. The median time-to-event will be presented where possible, along with the range and the associated two-sided 95% Brookmeyer-Crowley confidence interval. The event-free rate with 95% CI using Greenwood's formula will be provided for selected time points (e.g., 1, 3, 6, 12 and 24 months). Plots of the Kaplan-Meier estimate for the duration of response will be presented by apaglutide dose levels and in total.

*4.3.9.10 Best Overall Response Rate By Day 91*

The best overall MAGIC score is defined as the best response recorded from the start of the treatment until either Day 91 or the start of additional systemic therapy for GI-aGVHD, whichever occurs first, with the following ranking between scores from best to worst: CR, PR, SD, MR, PD, "Other" (includes: Death, Treatment Failure, Missing).

The best overall Lower GI Response is defined as the best response recorded from the start of the treatment until either Day 91 or the start of additional systemic therapy for GI-aGVHD, whichever occurs first, with the following ranking between scores from best to worst: CR, PR, SD, PD, "Other" (includes: Death, Treatment Failure, Missing).

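### Time to partial and complete lower GI response is summarised among responders only, an undeclared departure from the protocol's Kaplan-Meier and cumulative incidence methods; separately, direct complete responders have no usable time to PR

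*SAP*

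**What the plan says.** Protocol 1.5.2.2 lists time to partial and time to complete lower GI response as secondary endpoints. The first reads "Time to partial lower GI-aGVHD response (median and range) as defined by the MAGIC score". Protocol 7.8.2 sets the method: "Secondary endpoints assessed as time-to-event endpoints will be summarized using Kaplan-Meier analysis", and then "Where there are competing risks, time to event data will also be summarized using cumulative incidence". The synopsis agrees: "Secondary endpoints measured as time-to-event will be summarized using Kaplan-Meier analysis".

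SAP 4.3.9.8 measures each time from the first apraglutide injection to the first assessment showing that response. For PR it adds "This is only defined for subjects with partial response", and for CR "This is only defined for subjects with complete response". The summary, by dose level and in total, is a descriptive list: "number and percentage of subjects with partial and complete response, the arithmetic mean, standard deviation (sd), median, first and third quartiles (Q1, Q3), minimum, and" (the list closes with the largest value). No Kaplan-Meier estimate, confidence interval, cumulative incidence or censoring rule is given, although SAP 4.1.2 promises "Censoring for time-to-event endpoint will be described for each endpoint separately".

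SAP Section 6 lists 12 changes from the protocol analyses. The nearest, items 8 and 9, concern the confidence level of the medians and the follow-up needed for duration of response. None concerns time to PR or CR.

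**The concern.** A time-to-event summary restricted to subjects who had the event conditions on the outcome. Its median answers how long responders took, given that they responded. It does not answer how soon a treated subject can expect to respond, because subjects without a response contribute no time. Two doses with quite different response rates can therefore show the same median.

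A second, separate problem lies in the definition. SAP 4.3.9.2 puts each lower GI assessment in exactly one category, so PR and CR are exclusive at a visit, and time to PR runs to the first PR assessment. A subject who moves straight to CR and stays there has no PR time. If that subject later slips to PR, the recorded PR time falls after the CR time. Faster and deeper response can thus remove the early values from the time-to-PR row.

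At stake is how a secondary, descriptive speed-of-response result is read, particularly when low and high dose appear side by side.

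**Working it through.** The plan states no figure for this endpoint and the documents contain no event times, so there is nothing to reproduce. The check is a comparison of texts followed by constructed examples.

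**Does the Kaplan-Meier rule cover this endpoint?** Protocol 7.8.2 does not name time to PR or CR, and the endpoint carries the words median and range. Duration of response from Day 28 and Day 56 carries the same words in Protocol 1.5.2.2, and SAP 4.3.9.9 still analyses it by Kaplan-Meier. The wording is therefore no exemption.

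**Are there competing risks?** Under ICE1 and ICE4 in SAP 4.3.9.2, death and additional systemic therapy set the subject to non-response from that point to the Primary Analysis cut-off. No first response can be recorded in that period, so both act as competing events in the SAP's own terms.

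**Who can have a PR time?** Protocol 2.2 and inclusion criterion 5 admit lower GI Stage 1 to 4. PR is a one-stage improvement (SAP Appendix A). From Stage 1 that is Stage 0, which is CR. A Stage 1 baseline subject can therefore never have a PR time.

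**Illustration 1, conditioning on response (assumed data).** One arm of 15, followed to Day 91, with three deaths without response at Days 20, 35 and 50. The remaining non-responders are censored at Day 91.

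- Kaplan-Meier with deaths censored: S(t) = product of (1 − r/n), where r is responses and n is the number at risk at each response day.
- Cumulative incidence: sum of S_all(t−) × r/n, where S_all counts responses and deaths as events. With no censoring before Day 91 this equals responders to date divided by 15.

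Case (a), responses at Days 7, 14, 14, 14, 28, 28, 42, 56, 56:

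S(91) = (14/15) × (11/14) × (8/10) × (6/7) × (3/5) = 0.302, so 1 − S = 69.8%. At Day 42, 1 − S is 49.7%, so the Kaplan-Meier median is Day 56. Cumulative incidence is 7/15 = 46.7% at Day 42 and 9/15 = 60.0% at Day 56.

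Case (b), responses at Days 7, 14, 14, 28, 42, 56:

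S(91) = (14/15) × (12/14) × (10/11) × (8/9) × (6/7) = 0.554.

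Case (c), responses at Days 7, 28, 56:

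S(91) = (14/15) × (12/13) × (9/10) = 0.775.

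| Case | Responders | Responder-only median | Kaplan-Meier median | 1 − KM, Day 91 | Cumulative incidence, Day 91 |
|---|---|---|---|---|---|
| a | 9/15 | 28 days | 56 days | 69.8% | 60.0% |
| b | 6/15 | 21 days | not reached | 44.6% | 40.0% |
| c | 3/15 | 28 days | not reached | 22.5% | 20.0% |

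The responder-only median does not follow the fall in response from 60% to 20%. With these deaths, 1 − KM exceeds cumulative incidence by 9.8, 4.6 and 2.5 points, which is why the protocol's second sentence matters.

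**Illustration 2, direct complete response (assumed data).** Nine of 15 respond. If five reach PR at Day 14 and four reach PR at Day 28, the median time to PR is the fifth of nine values, 14 days. Now let the same five go straight to CR at Day 14 and stay there. Only the four Day 28 values remain, so the median time to PR becomes 28 days. First response of either kind is unchanged: 5/15 = 33.3% by Day 14 and 9/15 = 60.0% by Day 28.

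**The case against.** The best defence is that the response information is not lost. The table in 4.3.9.8 prints the number and percentage with PR and CR beside the median. SAP 4.3.9.2 reports Full Analysis Set response rates by visit, with missing assessments as non-response, and plots the lower GI rate over time. SAP 4.3.9.10 tabulates best response by Day 91, with deaths and treatment failures shown. In Illustration 2 the five direct complete responders have a time to CR of Day 14 in the same section. All of this stands, and it means a careful reader would not be misled about how many responded. What is missing is an all-subject description of when they first responded: visit-level rates are not cumulative, and they do not repair the PR median.

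Protocol 7.8.2 also opens by saying that secondary endpoints are summarised descriptively, makes cumulative incidence conditional, and names graft failure and non-relapse mortality rather than response. That weakens the cumulative incidence part of the departure, which rests on reading ICE1 and ICE4 as competing events. It does not remove the general Kaplan-Meier sentence.

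Three stronger readings are tempting but unsupported.

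- A reader might infer that all subjects who die or are rescued drop out. Only those with no earlier response do; a subject who responded first keeps that time.
- A reader might blame the direct-to-CR gap on the SAP abandoning the protocol's method. Separate times to PR and CR are the protocol's own endpoints, and it gives no rule for these subjects either.
- A reader might conclude that the median is uninformative. It does describe responders, and is incomplete rather than empty.

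**Conclusion.** The point holds as a minor one, in two parts. First, SAP 4.3.9.8 replaces the protocol's Kaplan-Meier, and cumulative incidence where risks compete, with responder-only descriptives, and Section 6 does not say so. The resulting median does not describe how fast treated subjects respond. Second, time to PR is ill-defined for subjects who go directly to CR and cannot be observed from a Stage 1 baseline. That is a definition flaw shared with the protocol, not a departure from it.

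The real size cannot be computed. The illustrations rest on assumed response and death times in arms of 15, and the share of direct complete responders is unknown. The consequence is limited because the endpoint is secondary and descriptive, response counts and rates are reported alongside, and Section 6 item 12 says no formal dose comparison will be made.

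**What to change.** In SAP 4.3.9.8, report for the Full Analysis Set, by dose and in total, the cumulative incidence from first dose of (i) first lower GI response, PR or better, and (ii) CR. Treat death and additional systemic therapy before response as competing events, in line with ICE1 and ICE4. Censor other subjects without the response at their last MAGIC assessment. Show the protocol's Kaplan-Meier estimate alongside. Label PR or better as a supplementary definition, since the protocol does not list it.

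Keep the responder-only table as supportive, and state there that direct complete responders and Stage 1 baseline subjects have no PR time unless a direct complete responder later slips to PR. List any remaining departure in Section 6 with its reason.

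The cost is one extra standard analysis on data already collected, one supplementary endpoint definition and a few lines of SAP text.

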#### *4.3.9.11 Incidence of malignancy relapse up to 2 years post-first dose of apaglutide*

The malignancy relapse/progression time is defined as the time from the date of the first dose to the date of hematologic malignancy relapse/progression.

Hematologic malignancy relapse/progression will be identified by manual review of reported malignancies or relapses in the AE data against the Underlying disease history CRF by the medical team, and confirmed with Sponsor. The list of identified hematologic malignancy relapse/progression will be finalized prior to the data base lock both for the Primary and the EOT analysis.

The malignancy/relapse progression will be summarized using Kaplan-Meier estimator. The number and percentage of subjects experiencing an event, and subjects censored will be summarized by apaglutide dose levels and in total. The median time-to-event will be presented where possible, along with the range and the associated two-sided 95% Brookmeyer-Crowley confidence interval. The event-free rate with 95% CI using Greenwood's formula will be provided for selected time points (e.g., 1, 3, 6, 12 and 24 months).

Plots of the Kaplan-Meier estimate for the malignancy/relapse progression will be presented by apaglutide dose levels and in total.

Subject for which no malignancy/relapse progression event occurs will be right censored at their last follow-up visit.

Incidence of malignancy/relapse progression will be analyzed only for the EOT analysis.

*4.3.9.12 Overall Survival up to 2 years post-first dose of apaglutide*

The overall survival time is defined as the time from the date of the first dose to the date of death due to any cause.

The last date known to be alive for each individual subject may be determined using, but not limited to, the following dates recorded on the eCRF:

- AE start and stop dates
- Study treatment start and stop dates
- Sample collection date for laboratory assessments
- Dates of any performed visit
- Start and stop dates of concomitant medications

Subjects who are alive at the time of data cut-off will be right censored on the date the subject was last known to be alive.

The overall survival time will be summarized using Kaplan-Meier estimator. The number and percentage of subjects experiencing an event (death), and subjects censored will be summarized by apaglutide dose levels and in total. The median time-to-event will be presented where possible, along with the range and the associated two-sided 95% Brookmeyer-Crowley confidence interval.

Plots of the Kaplan-Meier estimate for the overall survival will be presented by apaglutide dose levels and in total.

Overall Survival will be analyzed only for the EOT analysis.

*4.3.9.13 Non-relapse Mortality up to 2 years post-first dose of apaglutide*

The non-relapse mortality time is defined as the time from the date of the first dose to the date of death not preceded by hematologic malignancy relapse/progression.

The non-relapse mortality will be summarized using Kaplan-Meier estimator. The number and percentage of subjects experiencing an event, and subjects censored will be summarized by apaglutide dose levels and in total. The median time-to-event will be presented where possible, along with the range and the associated two-sided 95% Brookmeyer-Crowley confidence interval. The event-free rate with 95% CI using Greenwood's formula will be provided for selected time points (e.g., 1, 3, 6, 12 and 24 months).

Plots of the Kaplan-Meier estimate for the non-relapse mortality will be presented by apraglutide dose levels and in total.

Subject for which “hematologic malignancy relapse/progression” event occurs will be right censored at the time of occurrence of the event.

Subject for which neither “death” or “hematologic malignancy relapse/progression” event occurs will be right censored at their last follow-up visit.

